# **Missing Values**

In order to assess the impact of missing data on the conclusion of the primary analysis sensitivity analysis of the primary efficacy endpoint will be performed on the population of all randomised subjects. Details are provided in section 3.2.4.1.

3.2.2.3 Secondary Efficacy Analysis

The first secondary efficacy endpoint is the mean PGA score at Treatment Cycle 1, Week 6.

This endpoint will be analysed using an Analysis of Variance (ANOVA) on the rank. This model will include treatment group, the two stratification factors and the pooled centre as fixed covariates.

For handling of multiplicity see section 3.1.5.

LS Means together with their SE and 95% CI will be provided for the rank values of each treatment group. The LS means on the original scale will be presented as well as the estimate of the magnitude of the back transformed difference between the treatment groups (for any of the two tested doses of Dysport (8 U/kg and 16 U/kg), the LS mean of the back transformed difference Dysport tested dose - Dysport 2 U/kg) and the associated p-values. Additionally, for all other effects taken into account in the ANOVA the respective type III test p-value will be presented. The SAS® code for this model is as follows:

proc mixed data =  $\langle xxx \rangle$ ;

class Treatment age range BTX stratum centre;

model rank\_score = Treatment age\_range BTX\_stratum centre / solution cl;
/\* contrast analyses \*/

estimate 'Dysport 16 U/kg versus Dysport 2 U/kg' Treatment -1 0 1/cl;

estimate 'Dysport 8 U/kg versus Dysport 2 U/kg' Treatment -1 1 0/cl;

/\* Adjusted means and 95% CI by treatment group \*/

lsmeans Treatment/ cl ;

```
ods output SolutionF = SolutionF Tests3 = Tests3
Estimates = Estimates LSMeans = LSMeans;
run;
quit;
```

The second secondary efficacy endpoint is the mean GAS score at Treatment Cycle 1, Week 6. This endpoint will be analysed using an ANOVA on the GAS score. This model will include treatment group, the two stratification factors and the pooled centre as fixed covariates. Same output will be presented as for mean PGA.

# 3.2.2.4 Sensitivity Analyses for the First Secondary Efficacy Endpoint

## **Robustness (Proportional Odds Model)**

To check the robustness of the rank ANOVA analysis, a sensitivity analysis will be performed using the POM. This analysis will be applied to the ordered PGA categorical responses and the resulting odds ratio measures the relative probability of a better PGA response on Dysport (8 and 16 U/kg) as compared to Dysport 2 U/kg. An odds ratio > 1 for Dysport (8 and 16 U/kg) versus Dysport 2 U/kg indicates a positive treatment effect in favour of Dysport (8 and 16 U/kg), and an odds ratio <1 indicates a treatment effect in favour of Dysport 2 U/kg. This model will include treatment group, the two stratification factors (age range and BTX treatment naive status at baseline) and the pooled centre as fixed covariates. The odds ratios will be presented together with their 95% CI and the associated p-value. Additionally, for all other effects taken into account in the POM, the respective type III test p-value will be presented.

The following SAS® code will be used to compare the Dysport (8 U/kg and 16 U/kg) versus Dysport 2 U/kg.

proc logistic data = <xxx> order = internal;

class Treatment (ref 'Dysport 2 U/kg') age\_range BTX\_stratum centre / param = ref;

model score (descending) = Treatment age\_range BTX\_stratum centre / clodds = wald;

oddsratio 'Treatment' Treatment / cl wald;

/\* contrast analyses \*/

contrast 'Dysport 16 U/kg versus Dysport 2 U/kg' Treatment 1 0/ e estimate = exp;

contrast 'Dysport 8 U/kg versus Dysport 2 U/kg' Treatment 0 1/ e estimate = exp;

/\* p-values and odds ratio by treatment group \*/

ods output Nobs = Nobs Oddsratioswald = Oddsratios Contrastestimate = Contrasts Type3 = Type3 ConvergenceStatus = convstat CumulativeModelTest = Propval;

run;

quit;

In addition, a summary table will present the number and percent of subjects within each response category at Week 6 by treatment group.

## **Missing Values**

In the view of registration in US only, two sensitivity analyses of the first secondary efficacy endpoint will be performed on the population of all randomised subjects in order to assess the impact of missing data on the conclusion. Details are provided in section 3.2.4.1.

# 3.2.2.5 Tertiary Efficacy Analysis

For tertiary efficacy endpoints summary tables will present descriptive statistics across all treatment cycles for fixed dose Treatment Cycle 1 as well as for repeat Treatment Cycles. For fixed dose Treatment Cycle 1 tertiary efficacy endpoints will be analysed in addition according to their scale (categorical or continuous), using ANCOVA/ANOVA on the rank, ANCOVA or Logistic regression for Treatment Cycle 1 up to Week 16 (inclusive). For any additional visits of Treatment Cycle 1 (any visits after Week 16) and also for all analyses by repeat Treatment Cycle, only descriptive statistics will be performed.

In the following list, the term 'all post-treatment visits' refers to data from each visit at each treatment cycle (Treatment Cycles 1, 2, 3 and 4), unless it is specifically stated that it relates only to visits from the fixed dose Treatment Cycle 1. Also where the term 'except Week 6' is utilised for analyses of Treatment Cycle 1, it only means that this is already a specified primary or secondary endpoint, not that it will not be analysed.

- Mean change from Baseline to all post-treatment visits of Treatment Cycle 1 (except Week 6) in MAS score in the Treatment Cycle 1 PTMG: ANCOVA model on ranked changes with treatment group, the baseline MAS score, the two stratification factors (age range and BTX naïve or non-naïve status as assessed at baseline), and the centre as fixed effects.
- CCI
- Mean change from Baseline to all post-treatment visits in MAS score in each injected muscle group (elbow, wrist and finger flexors) of the study limb: ANCOVA model on ranked changes with treatment group, the baseline MAS score in the injected muscle group, the two stratification factors, and the centre as fixed effects for Treatment Cycle 1; descriptive statistics for analyses by Treatment Cycle 1 to 4.

| • | CCI |
|---|-----|
|   |     |
|   |     |
|   |     |
|   |     |
| • | CCI |
|   |     |
|   |     |
|   |     |
| • | CCI |
|   |     |
|   |     |

- Mean PGA score at all post-treatment visits (except Treatment Cycle 1, Week 6): ANOVA model on the rank with treatment group, the two stratification factors, and the centre as fixed effects for Treatment Cycle 1; descriptive statistics for analyses by Treatment Cycle 1 to 4.
- Mean GAS score at all post-treatment visits (except Treatment Cycle 1, Week
   6): ANOVA model on the GAS score with treatment group, the two stratification factors, and the centre as fixed effects for Treatment Cycle 1; descriptive statistics for analyses by Treatment Cycle 1 to 4.

40/108

SAP Final Version 2.0: 19 Oct 2018

• Mean change from Baseline to both post-treatment PedsQL scores (Generic core scale and CP module); ANCOVA model with treatment group, the baseline score, the two stratification factors, and the centre as fixed effects for Treatment Cycle 1; descriptive statistics for analyses by Treatment Cycle 1 to 4.

For ANCOVA/ANOVA models on the rank the same output will be presented as described in 3.2.2.1 and 3.2.2.3.

In ANCOVA models on the non-transformed original values an estimate of the magnitude of the difference between the treatment groups (Least Square Means Difference Dysport dose (8 U/kg and 16 U/kg) Dysport 2 U/kg) will be presented

together with a p-value and a 95% CI to illustrate the precision of the estimated treatment groups' difference. Least Square Means together with their SE and 95% CI will also be reported in each treatment group. Additionally, for all other effects but the centre taken into account in the ANCOVAs, the respective type III test pvalue will be presented.

Logistic regression analyses will be run using the PROC LOGISTIC procedure with a Type III test. The odds ratios between the treatment groups (Dysport dose (8 U/kg and 16 U/kg) / Dysport 2 U/kg) will be presented together with a p-value and a 95% CI.

Additionally, for all other effects but the centre taken into account in the logistic regression models, the effect estimate, its 95% CI and the respective p-value for the significance testing will be presented.

The SAS® code for these models is as follows:

proc logistic data=data-set;

class Treatment (ref 'Dysport 2 U/kg') age range BTX stratum centre; model response variable (event='1') = Baseline Treatment age range BTX stratum centre/ clodds=wald; oddsratio 'Treatment' Treatment / cl=wald;

run; quit;

The absence of responders (or of non-responders) in a given centre can lead to convergence issues. If a convergence issue appears, the logistic regression model won't take into account the parameter centre.

The centre effect will be described in tables showing the proportion of responders and non-responders by centre.

In addition, a shift table from baseline to each visit will be presented for the MAS score and TS spasticity grade (Y).

For the GAS responder an analysis for the primary goal will also be performed. A subject will be defined as a responder if their primary goal (identified as "very important") reaches an outcome of 0 (expected outcome) or higher at any time posttreatment during the treatment cycle. The proportion of GAS responders will be evaluated using a logistic regression model with treatment group, age range, BTX naïve or non-naïve status as assessed at baseline and the centre as explanatory variables, using the LOGISTIC code above. The responder analysis will be repeated on the number of subjects who reached for their primary goal an outcome of 1 (somewhat more than expected outcome) or higher as well as an outcome of 2 (much more than expected outcome).

A responder analysis will also be performed on each of the goals, using those subjects who selected the specified goal (regardless of whether it was their primary goal) and the rating of the goal during the treatment cycle. Due to the low number of subjects per goal, only descriptive statistics will be provided.

For each goal, the number and percentage of subjects with each rating will be tabulated by baseline importance and difficulty and in total. The number and percentage of subjects choosing each goal at baseline of each Treatment Cycle will be tabulated by importance and difficulty and in total for each Treatment Cycle.
42/108

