At Week 16, subjects will be assessed for their eligibility to receive the next treatment. Subjects who are eligible for retreatment will be given the next treatment. Any subjects not eligible for retreatment will be evaluated every 6 weeks \pm 2 weeks in additional visits until they are eligible for retreatment.

Each subject will participate in the study for 1 year to 1 year and 9 months depending on the number of treatments administered and the treatment intervals. The duration of the follow up period will be dependent upon the treatment interval as follows:

- All subjects whose first three treatment intervals fall between ≥ 16 and ≤ 22 weeks will receive four treatments and will exit the study as soon as a new injection is required and no later than 22 weeks after last injection (up to a maximum of 1 year and 9 months study duration).
- All other subjects will not be given any further study treatment after Week 52 and will exit the study after 16 weeks of follow up of the last treatment.

CCI

The efficacy and safety of Dysport will be continuously assessed throughout the study. An independent Data and Safety Monitoring Board (DSMB) will be put in place and will monitor the safety in this study. At any point during the study and after review of the available data, the DSMB may recommend that the study is stopped based on safety data. Further details are provided in Section 13.6.1.

4.1.4 *Stopping Rules and Discontinuation Criteria*

The DSMB can recommend that the study (or any individual subject participation) is stopped at any time based on safety data (see Section 13.6.1).

In addition, subjects will be discontinued if:

CCI

For other reasons for withdrawal or discontinuation, see Sections 4.1.5 and 6.4.

4.1.5 *Early Study Termination*

The Sponsor may terminate this study at any time. Reasons for termination may include, but are not limited to, the following:

- The incidence or severity of AEs in this and/or other studies point to a potential health hazard for study subjects.
- Insufficient subject enrolment.
- Any information becoming available during the study that substantially changes the expected benefit risk profile of the study treatments.

- Recommendation by the DSMB.

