- Concomitant medications.
- Concomitant nondrug therapies.
- Physiotherapy and occupational therapy (frequency and intensity).
- Home exercises (frequency).
- Use of splints and/or orthoses.
- Vital signs (BP and HR) and body weight and height.
- Physician's Global Assessment Scale.
- Goal Attainment Scale.
- CCI [REDACTED]
- CCI [REDACTED]
- Collection of AEs.
- Eligibility for retreatment. Any subjects not eligible for retreatment will be evaluated every 6 weeks ±2 weeks in additional visits until they are eligible for retreatment (see Section 7.2.6).

7.2.6 *Additional Visits*

Any subjects not eligible for retreatment, at Week 16 of any treatment, will be evaluated every 6 weeks ±2 weeks in additional visits until they are eligible for retreatment. All subjects whose first three treatment intervals fall between ≥ 16 and ≤ 22 weeks will receive four treatments and will exit the study as soon as a new injection is required and no later than 22 weeks after last injection (up to a maximum of 1 year and 9 months study duration). All other subjects will not be given any further study treatment after Week 52 and will exit the study after 16 weeks of follow up of the last treatment.

The following assessments will be performed at each additional visit:

- Concomitant medications.
- Concomitant nondrug therapies.
- Physiotherapy and occupational therapy (frequency and intensity).
- Home exercises (frequency).
- Use of splints and/or orthoses.
- Vital signs (BP and HR).
- Physician's Global Assessment Scale.
- Goal Attainment Scale.
- CCI [REDACTED]
- CCI [REDACTED]
- Collection of AEs.
- Eligibility for retreatment. Any subjects not eligible for retreatment will be evaluated every 6 weeks ±2 weeks in additional visits until they are eligible for retreatment.

7.2.7 *End of Study or Early Withdrawal Follow up Visit*

At the end of study visit or early withdrawal the following assessments will be performed (±2 weeks):

- Concomitant medications.
- Concomitant nondrug therapies.
- Physiotherapy and occupational therapy (frequency and intensity).
- Home exercises (frequency).

- Use of splints and/or orthoses.
- Physical examination.
- Vital signs (BP and HR) and body weight and height.
- A 12-lead ECG.
- Blood sampling for BTX-A-Ab testing.
- Blood sampling for clinical chemistry (including serum ALP - total and bone isoenzyme, and HbA1c).
- Physician's Global Assessment Scale.
- Goal Attainment Scale.
- CCI [REDACTED]
- CCI [REDACTED]

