The GAS for each goal will be evaluated post-baseline at Week 6 and Week 16 of each Treatment Cycle, and also at the EOS/EW, and the total GAS score will be calculated using the formula in Section 3.2.13.20. A total GAS score of 50 means all individual goals have been achieved as expected.

Paediatric Quality of Life (PEDsQL) Inventory: Parents/guardians will be asked to complete questionnaires on their child's QoL [15] at each post-treatment visit to the study centre except Week 6. The PedsQL parent inventory measures healthcare concepts for children/adolescents of ages 2 to 18 years of age [16]. The Generic Core Scales cover four multidimensional scales including physical, emotional, social and school aspects with three

summary scales of total scale score, physical health summary score and psychosocial health summary score.

Parents/guardians will also complete the Condition-specific Module in CP (in countries where translation is available) [16], which is a complement to the Generic Core Scale of the PedsQL. It is designed to provide greater measurement sensitivity for circumscribed populations. The answers to the questionnaire will be obtained at baseline, at Week 16 of Treatment Cycle 1, and at the EOS/EW.

- For each defined scale a score is calculated using the transformations in Section 3.2.13.21.
- 1.3.2.2 Safety Assessments
  - Adverse Events (AEs): Collected from the signing of informed consent up until the EOS.
  - Physical examination: A physical examination will be carried out by a physician or by another qualified staff member designated by the Investigator at the screening visit and at the EOS/EW. If in the opinion of the Investigator there are any clinically significant changes in the physical examination findings (abnormalities) they will be recorded as AEs.
  - Vital signs: Systolic and diastolic blood pressure (BP), and heart rate (HR) will be measured at each visit to the study centre. Blood pressure will be measured with the subject in a sitting position.
  - Electrocardiogram (ECG): Subjects will have a set of three 12-lead ECG recordings taken at the screening visit (considered as baseline assessment), then subsequently one 12-lead ECG at Treatment Cycle 1, Week 6 and at the EOS/EW. The 12-lead ECG recordings will be performed at a paper speed of 25 mm/sec, recorded with the subject supine. Analysis of the ECG results will be performed in a central laboratory.

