#### SAP Final Version 2.0: 19 Oct 2018

# 3.1.6 Significance Testing and Estimation

## Fixed Dose Treatment Cycle 1

Apart from tests described in section 3.1.5, all statistical tests performed on the fixed dose Treatment Cycle 1 efficacy endpoints will be conducted, unless otherwise specified, at a two-tailed  $\alpha$  level of 0.05 and each tested Dysport dose group (8 U/kg and 16 U/kg) will be compared to Dysport 2 U/kg separately. Statistical tests will be performed on the efficacy endpoints for Treatment Cycle 1, up to Week 16 (inclusive), no statistical tests will be performed for any additional visits of Treatment Cycle 1 (any visits after Week 16).

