# Repeat Treatment

For the analyses by Treatment Cycle no statistical testing will be performed.

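### The GAS responder flag has no visit cap although Cycle 1 testing stops at Week 16, so, derived as written, later retreatment gives a child more chances to respond

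*SAP*

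**What the plan says.** SAP 3.2.2.5 (Tertiary Efficacy Analysis) defines a primary-goal GAS responder as a child whose goal "reaches an outcome of 0 (expected outcome) or higher at any time posttreatment during the treatment cycle". The definition names no last visit. The next sentence puts the flag in a logistic regression with treatment group, age range, toxin-naive status and centre. The analysis is then repeated for outcomes of at least 1 and for an outcome of 2, so three analyses rest on the same definition.

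Earlier in the section, tertiary endpoints are to be modelled "using ANCOVA/ANOVA on the rank, ANCOVA or Logistic regression for Treatment Cycle 1 up to Week 16 (inclusive", with descriptive statistics only for later Cycle 1 visits and for repeat cycles. SAP 3.1.6 agrees: "no statistical tests will be performed for any additional visits of Treatment Cycle 1 (any visits after Week 16". For repeat treatment it adds: "For the analyses by Treatment Cycle no statistical testing will be performed".

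On when GAS is rated, SAP 1.3.2.1 states: "The GAS for each goal will be evaluated post-baseline at Week 6 and Week 16 of each Treatment Cycle, and also at the EOS/EW". Protocol 7.2.6 goes further: "Any subjects not eligible for retreatment, at Week 16 of any treatment, will be evaluated every 6 weeks ±2 weeks in additional visits", and GAS is on the list of assessments for each of those visits.

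**The concern.** The number of GAS ratings in a cycle is not fixed by design. It grows with the time to retreatment. An endpoint that counts the best rating over the whole cycle therefore gives children with long cycles more opportunities to succeed, whatever their chance at a single visit. If arms differ in time to retreatment, part of any difference in responder rates would reflect the number of looks. The model has no term for this, and could not simply be given one, because cycle length arises after randomisation.

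The SAP does not say whether its Week 16 limit on testing also truncates this flag. The limit is written in terms of visits, whereas the flag summarises a cycle and belongs to no single visit. A programmer could observe the limit in every by-visit model and still derive the flag over the full cycle.

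**Working it through.** The documents give no responder rate, power or sample size for this endpoint, so there is no stated figure to reproduce.

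**Ratings per cycle.** The count is two (Weeks 6 and 16) plus one for each further six weeks. The day of retreatment normally coincides with the last visit of the previous cycle (Protocol 7.2.4).

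| Retreated at week | 16 | 22 | 28 | 34 | 52 |
|---|---|---|---|---|---|
| GAS ratings | 2 | 3 | 4 | 5 | 8 |

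**Chance of being a responder.** With per-visit probability p and k independent ratings, the chance is 1 − (1 − p)^k. For p = 0.30:
- k = 2: 1 − 0.70² = 51.0%
- k = 3: 1 − 0.70³ = 65.7%
- k = 4: 1 − 0.70⁴ = 76.0%

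Ratings of one goal in one child will be correlated, so independence is an upper bound on the gap. For correlated ratings the same expression was averaged over a normal effect shared within the child. The values of p and the correlations are assumptions.

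| Latent correlation | p = 0.30: 2 / 3 / 4 visits | p = 0.20: 2 / 3 / 4 visits |
|---|---|---|
| 0 | 51.0 / 65.7 / 76.0% | 36.0 / 48.8 / 59.0% |
| 0.5 | 44.3 / 53.0 / 59.0% | 31.3 / 38.9 / 44.4% |
| 0.8 | 38.9 / 43.9 / 47.2% | 27.1 / 31.3 / 34.3% |
| 0.9 | 36.2 / 39.6 / 41.9% | 25.0 / 27.8 / 29.8% |

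**Effect on a comparison of arms.** These figures compare children, not arms. To move to arms, assume:
- the same per-visit chance (p = 0.30) in both arms, so there is no true per-visit effect;
- four visits for 10% of the 2 U/kg arm and 50% of an active arm, and two visits for everyone else;
- 70 per arm, as planned;
- a two-sided 5% normal test of two proportions with unpooled standard error, standing in for the adjusted logistic model.

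Under independence the arm rates are 0.9 × 51.0 + 0.1 × 76.0 = 53.5% and 0.5 × 51.0 + 0.5 × 76.0 = 63.5%. The standard error is √(0.535 × 0.465/70 + 0.635 × 0.365/70) = 0.083, and the rejection rate is 22.6%.

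| Correlation | Arm rates | Spurious difference | Odds ratio | Rejection |
|---|---|---|---|---|
| 0 | 53.5 vs 63.5% | 10.0 points | 1.51 | 22.6% |
| 0.5 | 45.8 vs 51.7% | 5.9 points | 1.27 | 10.7% |
| 0.8 | 39.7 vs 43.1% | 3.3 points | 1.15 | 6.9% |
| 0.9 | 36.8 vs 39.1% | 2.3 points | 1.10 | 5.9% |

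With 10% against 30% having four visits, the rejection rates are 9.2%, 6.4%, 5.5% and 5.2%.

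**With the flag capped at Week 16.** Every child has the same two scheduled ratings. In this set-up the difference is 0, the odds ratio is 1.00 and the rejection rate is 5%, whatever the cycle lengths.

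**The case against.** The strongest reply is that the plan already contains the cap. SAP 3.2.2.5 names logistic regression among the methods limited to Week 16, and SAP 3.1.6 repeats the limit. On that reading the definition only says what response within a cycle means, and the other passages set the tested window. This is a fair reading, and under it the tested dose comparison is not affected. But the definition does not say so, whereas SAP 3.2.2.6 does state a Week 16 limit for the figures.

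Secondly, nothing visible says that cycle length differs by dose. The detailed reinjection criteria in Protocol 9.1.3.6 are redacted. Protocol 4.1.3 has four-treatment subjects leave once a new injection is needed, and SAP section 5 summarises time to retreatment by treatment group. A link to dose is therefore plausible, but it remains an inference, as does the direction of any bias.

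Thirdly, the calculation gives every child the same per-visit chance. Children with long cycles may be those with lasting benefit who reached the goal by Week 6 or 16, in which case extra visits would add few new responders. That stands, and is a further reason to treat the larger figures as upper bounds.

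Fourthly, responder rates in different cycles are not like for like in any case: goals are reset before each treatment, doses may change and nothing is tested in repeat cycles. That weakens the complaint about comparing cycles. It does not help a reader who compares dose groups within one repeat cycle.

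Finally, GAS is already analysed at fixed visits as a score. The word "also" is not needed to see that other responder analyses may exist: several bullets in SAP 3.2.2.5 are redacted, so a fixed-visit responder definition cannot be ruled out.

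**Conclusion.** The point holds as an unreconciled conflict with a conditional consequence. The responder definition runs over the whole cycle, while the testing rules stop at Week 16. If the flag is derived as the definition reads, the Cycle 1 dose comparison would be biased towards any arm with longer cycles. Even if the Week 16 limit is applied to the Cycle 1 model, that limit does not reach the descriptive responder rates in repeat cycles, which would still depend on cycle length.

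A reader might infer that the planned logistic comparison is biased, or biased in favour of the higher doses. The documents support neither statement: the first depends on which passage governs the derivation, and the second on redacted retreatment criteria.

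The size depends on the assumptions. At a 30% per-visit chance with 10% against 50% of children having four visits, false rejection runs from 22.6% under independence to 6.9% at correlation 0.8. The lower end is the more realistic for repeated ratings of the same goal. The endpoint is tertiary and was added in the SAP, so the primary and secondary conclusions are unaffected.

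**What to change.** In SAP 3.2.2.5, state that the primary-goal responder flag, at each of the thresholds 0, 1 and 2, uses only ratings up to and including the Week 16 visit of the cycle. Alternatively, define response at Week 6 and at Week 16 separately. Present later ratings descriptively, by visit and apart from the flag. Apply the same rule in every cycle, so that the repeat-cycle summaries also rest on equal scheduled opportunity.

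Either version agrees with the SAP's own testing window. The cost is a change of SAP wording and of the derivation, with no new data, and it should be made before unblinding.
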